- The US Food and Drug Administration granted approval to nivolumab for the treatment of unresectable or metastatic melanoma, advanced non-small cell lung cancer, renal cell carcinoma, Hodgkin's lymphoma, recurrent or metastatic squamous cell carcinoma of the head and neck, locally advanced or metastatic urothelial carcinoma, microsatellite instability-high or mismatched repair deficient metastatic colorectal cancer and hepatocellular carcinoma.
- The first randomized clinical trial in glioblastoma with nivolumab (CheckMate-143) was completed in early 2017. Unfortunately, the study didn't meet its primary endpoint of improved overall survival over bevacizumab monotherapy. The objective response rate (ORR) was lower in nivolumab arm than bevacizumab arm. However, the response with nivolumab was more durable. The safety profile of nivolumab was very consistent with what has been observed in other tumor types.

Objective:

- To determine the 6-month progression free survival rate in IDH-mutant gliomas patients with and without HMP in responses to nivolumab treatment.

Eligibility:

- Patients with diffuse glioma, confirmed by NCI Laboratory of Pathology
- Age ≥ 18 years,
- KPS $\geq 60\%$

- *IDH1* or *IDH2* mutation confirmed by DNA sequencing
- Patients must have TMB status performed at NIH
- Tumor tissue or slides should be available for molecular and immune profiling

Design:

- This study is an open label phase II clinical trial of the immune checkpoint inhibitor, nivolumab, in patients with HMP and NHMP IDH-mutant gliomas.
- Patients with HMP and NHMP will receive nivolumab at a standard dose of 240 mg intravenously every 2 weeks for cycles 1-2, then doses of 480 mg every 4 weeks for cycles 3-16. A maximum of 20 treatments will be given (16 cycles).
- A maximum of 29 patients with IDH-mutant glioma with HMP (Cohort 1) and 30 patients with NHMP (Cohort 2) will be evaluated.
- A Simon's optimal two-stage design will be used to conduct the HMP arm and the NHMP arm independently. For the HMP cohort, in stage I, a total number of 10 patients are accrued. If 9 or more patients progress by 6 months, the cohort will be terminated early; otherwise, additional 19 patients will be accrued in stage II, resulting in a total sample size of 29. Among these 29 patients, if 6 or more patients are progression-free at 6 months, we will claim that the treatment is promising for patients with HMP IDH-mutant gliomas. For NHMP cohort, in stage I, a total number of 15 patients are accrued. If 3 or more patients are progression-free at 6 months, the cohort will move to stage II and additional 15 patients will be accrued in stage II, resulting in a total sample size of 30. Among these 30 patients, if 10 or more patients are progression-free at 6 months, we will claim that the treatment is promising for patients with NHMP IDH-mutant gliomas.

TABLE OF CONTENTS

PRÉCIS.....	2
TABLE OF CONTENTS	4
STATEMENT OF COMPLIANCE	10
1 INTRODUCTION	11
1.1 Study Objectives	11
1.1.1 Primary Objective	11
1.1.2 Secondary Objectives	11
1.1.3 Exploratory Objectives	11
1.2 Background and Rationale.....	11
1.2.1 IDH mutation dictates glioma biology	11
1.2.2 IDH-mutant gliomas accumulate increased mutation burden during higher grade transformation.....	12
1.2.3 Cancers with high mutation burden better respond to checkpoint inhibitors	12
1.2.4 Nivolumab is used as an immune therapy for gliomas.....	13
1.2.5 Rationale for the patient-reported outcome studies	14
1.2.6 Rationale for the correlative studies with biospecimen.....	15
1.2.7 Rationale for changing sample number of NHMP cohort	15
2 ELIGIBILITY ASSESSMENT AND ENROLLMENT	16
2.1 Eligibility Criteria	16
2.1.1 Inclusion Criteria	16
2.1.2 Exclusion Criteria	17
2.1.3 Recruitment Strategies.....	18
2.2 Screening Evaluation	18
2.2.1 Screening activities performed prior to obtaining informed consent	18
2.2.2 Screening activities performed after a consent for screening has been signed.....	18
2.3 Participant Registration and Status Update Procedures.....	19
2.3.1 Screen Failures.....	19
2.3.2 Treatment Assignment Procedures (For registration purposes only):	19
2.4 Baseline Evaluation.....	20
3 STUDY IMPLEMENTATION	20

3.1	Study Design	20
3.2	Drug Administration	21
3.3	Dose Modifications	21
3.4	Questionnaires.....	27
3.5	Study Calendar.....	28
3.6	Cost and Compensation	32
3.6.1	Costs	32
3.6.2	Compensation	32

16 APPENDICES	67

16.1	Appendix A: Performance Status Criteria	67
16.2	Appendix B: Neurologic Evaluation.....	67
16.3	Appendix C: Management Algorithms For Endocrinopathy, Gastrointestinal, Hepatic, Neurological, Pulmonary, Renal, And Skin Adverse Events	69
16.4	Appendix D: RANO Criteria And iRANO Treatment Algorithm.....	76
16.5	Appendix E: Pregnancy Form.....	78

STATEMENT OF COMPLIANCE

The trial will be carried out in accordance with International Conference on Harmonisation Good Clinical Practice (ICH GCP) and the following:

- United States (US) Code of Federal Regulations (CFR) applicable to clinical studies (45 CFR Part 46, 21 CFR Part 50, 21 CFR Part 56, 21 CFR Part 312, and/or 21 CFR Part 812)

National Institutes of Health (NIH)-funded investigators and clinical trial site staff who are responsible for the conduct, management, or oversight of NIH-funded clinical trials have completed Human Subjects Protection and ICH GCP Training.

The protocol, informed consent form(s), recruitment materials, and all participant materials will be submitted to the Institutional Review Board (IRB) for review and approval. Approval of both the protocol and the consent form must be obtained before any participant is enrolled. Any amendment to the protocol will require review and approval by the IRB before the changes are implemented to the study. In addition, all changes to the consent form will be IRB-approved; an IRB determination will be made regarding whether a new consent needs to be obtained from participants who provided consent, using a previously approved consent form.

1 INTRODUCTION

1.1 STUDY OBJECTIVES

1.1.1 Primary Objective

- To determine the 6-month progression free survival rate in IDH-mutant gliomas patients with and without hypermutator phenotype (HMP) in responses to nivolumab treatment.

1.1.2 Secondary Objectives

- To determine the 1-year progression free survival rate and overall survival in IDH-mutant gliomas patients with and without HMP in response to nivolumab treatment.
- To determine whether the neoantigen burden in tumor prior to the treatment is correlated with treatment response.
- To longitudinally evaluate patient reported outcome measures using self-reported symptom severity and interference with daily activities using the MDASI-BT.

1.1.3 Exploratory Objectives

- To determine if a change in immunocompetence defined by peripheral blood mononuclear cell (PBMC) assays and phenotyping over the course of the study treatment correlates with the response and/or treatment-related toxicity.
- Evaluate the immune infiltrates profiles in the tumor microenvironment using quantitative immunofluorescences, digital spatial profiling (DSP) and/or RNA sequencing prior to treatment of nivolumab and correlate with treatment response.
- Measure T cell receptor (TCR) repertoire in PBMC, pre-nivolumab treatment and post every 2 cycles until progression to determine expansion of specific clones and correlation with response.
- Evaluate the epigenetic signatures in tumor samples at baseline and correlate with the mutation burden and treatment response by analyzing DNA methylation by the Infinium Methylation BeadChip.
- Evaluate the genomic features of cell free DNA in the peripheral blood pre-nivolumab treatment cycles 1,2, 3 and at disease progression

1.2 BACKGROUND AND RATIONALE

1.2.1 *IDH* mutation dictates glioma biology

Gliomas are the most common malignant brain tumors and nearly 17,000 people lose their lives to this disease every year. Genes encoding for isocitrate dehydrogenases 1 and 2, *IDH1* and *IDH2*, are frequently mutated in gliomas and they are the most commonly mutated metabolic genes that have been identified in human cancers [1-4]. The mutant *IDH1/2* causes loss of its normal function, the production of α -ketoglutarate (α -KG), and the gain of function to produce 2-hydroxyglutarate (2HG) [3, 5]. As a consequence of the mutation, IDH-mutant gliomas are unique phenotypically, genetically and epigenetically [6-8]. Therefore, the *IDH* mutation status was used as a major genetic marker to classify the diffuse astrocytic and oligodendroglia tumors by the most recent WHO Classification of Tumors of the Central Nervous System [9]. Glioma patients with mutant

IDH have better prognosis than those with wild type IDH [2] and some studies have provided the evidence to suggest that IDH-mutant gliomas are more sensitive to chemotherapy [10, 11].

1.2.2 IDH-mutant gliomas accumulate increased mutation burden during higher grade transformation

Despite the fact that patients with IDH-mutant gliomas survive longer, most tumors eventually go through higher grade transformation. In an integrated genomic analysis of the genetic and epigenetic basis for the malignant progression in IDH-mutant gliomas, the non-linear clonal expansion of the original tumors and new oncogenic pathways were identified in the same tumor at the time of malignant transformation [12]. A subset of recurrent tumors was found to be hypermutated and acquired the mutation in mismatch-repair genes. A recent study demonstrated that the mutant IDH1 downregulates the DNA damage sensor ATM by altering histone methylation, leading to impaired DNA repair[13]. As a DNA repair enzyme, α -KG-dependent alkB homolog (ALKBH) is suppressed by 2-HG as a consequence of *IDH* mutation. Cells expressing mutant IDH display reduced repair kinetics, accumulate more DNA damages [14].

Alkylating agents have been used as the major chemotherapy for gliomas, including the IDH-mutant gliomas. Temozolomide (TMZ) has been a commonly used chemotherapy for diffuse gliomas. However, the inherent vulnerability to DNA damage increased the likelihood of DNA damage accumulation in IDH-mutant gliomas. As with all other alkylating agents, TMZ adds a methyl group to the O6 guanine residue (O6-meG), which is primarily repaired in the cells by O6-methylguanine DNA methyltransferase (MGMT)[15]. The limited repair mechanism of O6-meG renders mismatch repair (MMR) pathway status a critical element to determine the fate of the tumor cells, where the intact MMR leads to cell death and loss of MMR function causes mispairing of guanine with thymine and resistance to TMZ[16, 17]. In the absence of MGMT repair and deficient MMR, C>T/G>A signature and TMZ resistance were found. In a mutational analysis, exposure to TMZ can increase the mutation rate at the time of tumor progression [18]. Post-TMZ recurrences had a 39- to 133-fold increase in the mutation rate relative to the treatment-naïve initial low grade tumor, more than 98 % of which are C>T/G>A mutations which are associated with TMZ-induced mutagenesis[19]. In a subset of TMZ-treated recurrent GBM that arose from IDH1-mutant low-grade astrocytoma, hypermutation was identified. The hypermutated tumors were found to acquire mutations in MMR pathway that were not detected in the initial tumors [18] and TMZ was suggested as a predominant source by the mutational signatures [20]. In summary, compromised DNA repair and the common therapeutic agents may contribute to malignant transformation and the development of a hypermutator phenotype in IDH-mutant gliomas.

1.2.3 Cancers with high mutation burden better respond to checkpoint inhibitors

Tumor mutation burden (TMB) can be affected by a variety of causes, including but not limited to the exposure to mutagens, such as TMZ, and deficient MMR. When TMB is high enough, it may be associated with an increased hyper sensitivity to the immune checkpoint inhibitors, potentially due to the expression of immune-reactive neo-antigens in the tumors. This concept has been proven in a variety of refractory cancers [21-23]. Many of the tumors that respond to immune checkpoint inhibitors have deficient mismatch repair (MMR) mechanisms, which leads to 10 to100 times as many somatic mutations as those with proficient MMR [24-26]. Moreover, findings that are consistent with immune response, such as lymphocyte infiltration was found in MMR deficient tumors [27, 28]. The connection between the presence of deficient MMR and better immune response was made, since the somatic mutation can be recognized by the immune system

[29]. There has also been an increasing body of evidence to suggest that the cancers exhibiting high TMB, such as bladder cancer, non-small cell lung cancer and melanoma, are responsive to check point inhibitors [30-32]. High mutation and neoantigen burden may also be associated with improved response to immune checkpoint inhibitor in gliomas[33]. Studies of GBM patients with biallelic mismatch repair deficiency (bMMRD), a cancer predisposition syndrome, demonstrated a high mutation burden in their tumors [33, 34]. In this study, authors have demonstrated that all high grade bMMRD tumors are hypermutant, harboring over 100 exon mutations averagely. In the neoantigen analysis, the mean neoantigen burden was seven to 16 times higher than those of immune responsive melanomas, lung cancers, and microsatellite-unstable GI cancers. The case report of a significant responses of recurrent multifocal GBM to nivolumab in two siblings who have bMMRD has provided appealing evidence to theory that checkpoint inhibitor can induce significant clinical responses.

Although the response to immune checkpoint inhibitors in IDH-mutant gliomas with increased mutational burden may differ from these hypermutated gliomas resulted from germline mutation, it is important to investigate this in patients with IDH-mutant gliomas. There are no studies investigating the concept that the tumors with high TMB better respond to immune therapy. The goal for this proposed clinical study is to proof this concept in IDH-mutant gliomas, which overall are immunogenic[35]. For the purpose of this study, we have adopted the same criteria that is used in FOUNDATIONONE™, an FDA-approved next-generation sequencing based assay for identification of genomic alterations within the cancer related genes, to define the hypermutator phenotype (HMP).

For this study, the HMP is defined as 5 somatic mutations/MB detected by CLIA -certified sequencing study at NCI.

1.2.4 Nivolumab is used as an immune therapy for gliomas

Although T cells within the central nervous system act in an antigen-dependent manner, they often have decreased cytotoxic function in the context of tumor [36, 37]. The tumor cell-induced inhibitory effect on T cells is one of important mechanisms. Programmed death-1 (PD-1) has been recognized as a checkpoint protein that is expressed on activated CD4+ and CD8+ T cells, B cells, monocytes, natural killer T (NKT) cells, and dendritic cells (DCs) [38]. B7-H1, which is also called PD-L1, is a co-stimulatory inhibitory molecule that was found to be expressed in malignant glioma [39]. When T cells expressing PD 1 encounter PD L1, T cell functions are subsequently diminished and cause immunosuppressive microenvironment.

Nivolumab is a monoclonal antibody that binds to the PD-1 receptor and blocks its interaction with PD L1 and PD L2 and subsequently releasing PD-1 pathway mediated inhibition of the immune response, including antitumor immune response. The US Food and Drug Administration granted approval to nivolumab for the treatment of unresectable or metastatic melanoma, advanced non-small cell lung cancer, renal cell carcinoma, Hodgkin's lymphoma, recurrent or metastatic squamous cell carcinoma of the head and neck, locally advanced or metastatic urothelial carcinoma, microsatellite instability-high or mismatched repair deficient metastatic colorectal cancer and hepatocellular carcinoma. The first randomized clinical trial in glioblastoma with nivolumab (CheckMate-143) was completed in early 2017. The purpose of the study was to compare the efficacy and safety of nivolumab administrated alone versus bevacizumab in patients diagnosed with recurrent glioblastoma, and to evaluate the safety and tolerability of nivolumab administered alone or in combination with ipilimumab in patients with different lines of the GBM

therapy. The primary outcome measure was overall survival (OS), and the secondary outcome included overall survival rate, progression-free survival (PFS), and objective response rate (ORR). The result was presented in May 2017. At the time of final analysis, 369 pts were randomized, where 182 received nivolumab and 165 received bevacizumab. At baseline, 40% patients received nivolumab and 43% of patients received bevacizumab required corticosteroids. The OS was 9.8 months with nivolumab and 10.0 months with bevacizumab, and the 12-mo OS rate was 42% in both arms. PFS medians were 1.5 months (nivolumab) and 3.5 months (bevacizumab). Among evaluable patients treated with nivolumab (n = 153) or bevacizumab (n = 156), ORRs were 8% (nivolumab) and 23% (bevacizumab); duration of response medians was 11.1 months (nivolumab) and 5.3 months (bevacizumab). Treatment-related AEs (TRAEs) occurred in 57% (nivolumab) and 58% (bevacizumab) of patients; the most common TRAEs ($\geq 10\%$ of patients in either arm; nivolumab vs bevacizumab) were fatigue (21% vs 14%) and hypertension (1% vs 22%). Grade 3–4 TRAEs were reported in 18% (nivolumab) and 15% (bevacizumab) of patients. Serious AEs (all causality) were reported in 46% (nivolumab) and 35% (bevacizumab) of patients; seizure (8% vs 6%) and malignant neoplasm progression (11% vs 7%) were the only serious AEs reported in $\geq 5\%$ of patients in either arm. AEs leading to discontinuation occurred in 10% (nivolumab) and 15% (bevacizumab) of patients. Unfortunately, the study did not meet its primary endpoint of improved overall survival over bevacizumab monotherapy. The ORR was lower in the nivolumab arm than the bevacizumab arm. However, the response with nivolumab was more durable. The safety profile of nivolumab was very consistent with what has been observed in other tumor types. [40]

NRG Oncology Foundation recently completed the phase I study of checkpoint inhibitors anti-CTLA-4, anti-PD-1, the combination in patients with newly diagnosed glioblastoma [41]. In this study, the treatment was started after concurrent chemoradiation therapy, along with adjuvant chemotherapy with TMZ. The primary endpoint was the dose limiting toxicity (DLT) from the start of immune checkpoint inhibitors (ICIs) to 8 weeks after in each arm. A standard up-and-down design was used, with 6 evaluable patients enrolled at a given dose level. The dose level would be declared safe if no more than 1 of 6 had an DLT. Among 31 analyzable patients, treatment was found well tolerated: no reported grade 5 events, 16% of grade 4 events. The study has demonstrated that ICIs including nivolumab are safe and tolerable with similar toxicity profiles noted with other cancers when given with adjuvant TMZ. The results provide necessary safety data justifying the performance of a subsequent trial to test the efficacy of ICIs in this disease.

1.2.4.1 Dosing schedule of nivolumab:

Studies performed in other cancers have demonstrated that after an induction period, the monthly dosing of nivolumab is equally effective but less taxing on patients. The population pharmacokinetics (PPK) and exposure response analyses have been performed to support the use of a nivolumab 240mg Q2W, 360 mg Q3W, and 480 mg Q4W dosing schedule in cancer patients in addition to 3mg/kg Q2W. 240mg Q2W was selected since it is identical to a dose of 3mg/kg for a subject weighing 80 kg, the observed median body weight in nivolumab-treated cancer patients. The Q3W and Q4W dosing schedule allow flexibility of dosing with less frequent visit, which is more convenient for cancer patients.

1.2.5 Rationale for the patient-reported outcome studies

Precedence for measuring “non-therapeutic” endpoints exists in oncology research. For example, Gemcitabine was approved by the FDA partially as a consequence of the decrease in pain reported in pancreatic patients who were treated, not on the basis of survival improvement, which was

modest, at best. There have been efforts in neuro-oncology to evaluate secondary endpoints using validated instruments as an additional indicator of benefit.

The M.D. Anderson Symptom Inventory-Brain Tumor Module allows the self-reporting of symptom severity and interference with daily activities. The MDASI-BT has demonstrated reliability and validity in the adult primary brain and spine tumor patient population. [42, 43] This tool represents a modification of the widely used and validated M.D. Anderson Symptom Inventory, with particular attention to symptoms common in patients with brain and spine tumors respectively.

The MDASI consists of symptoms rated on an 11-point scale (0 to 10) to indicate the presence and severity of the symptom, with 0 being “not present” and 10 being “as bad as you can imagine.” Each symptom is rated at its worst in the last 24 hours. Symptoms included on the instrument include those commonly associated with cancer therapies, those associated with increased intracranial pressure, and those related to focal deficits. The questionnaire also includes ratings of how much symptoms interfered with different aspects of a patient’s life in the last 24 hours. These interference items include general activity, mood, work (includes both works outside the home and housework), relations with other people, walking, and enjoyment of life. The interference items are also measured on 0 - 10 scales. The average time to complete these instruments is 5 minutes. The MDASI-BT has been translated into multiple languages, but the English language version will be used for this study. In addition, information regarding demographics and treatment history will be collected as part of the larger study and used in this analysis.

The availability of validated instruments provides an opportunity to prospectively assess the impact of treatment, both positive and negative, on patients. The evaluation of symptom burden in this study will assist in finding the best possible treatment with the least toxicity.

Evaluation of the symptom across the scores are an important endpoint for the study. Assessment during the course of treatment may provide important complementary outcome data, which allows the determination of the net clinical benefit of each treatment. The common adverse events associated with nivolumab may result in a measurable effect on patient’s well-being and quality of life and those impacts are unlikely to be captured by conventional measures of efficacy such as MR imaging.

1.2.6 Rationale for the correlative studies with biospecimen

The tumor microenvironment contains both tumor cells, which express immune regulatory molecules, and cells with cytolytic capacities. We hypothesize that the immune check point inhibitor conveys the antitumor effects through affecting the whole tumor microenvironment, whose profile is essential for the analysis of treatment response. In this study, we plan to collect both blood samples and tumor samples for the purpose of immune monitoring (See details in the Section 5). The results may provide insights into treatment responses or resistance and potentially lead to the rationale for combined therapies with nivolumab.

1.2.7 Rationale for changing sample number of NHMP cohort

Under the protocol version C (version date 12/09/2021), we performed an interim analysis after a total number of 15 NHMP patients were accrued. 6 patients are progression-free at 6 months. Per protocol, NHMP cohort should proceed to stage II and recruit additional 31 patients. When the characteristics of the 15 patients treated in this cohort were analyzed, 8 of the 15 patients had diagnosis of glioblastoma (WHO grade 4) prior to the study treatments, 6 with anaplastic glioma

(WHO grade 3) and only one with grade II glioma. The distribution of the tumor histology for this cohort was unexpected. The original sample size calculation of the current protocol was based on the expectation of grade III gliomas being the predominant histology, which led to setting the null hypothesis PFS6 being 0.3 (usually used for grade 3 gliomas) and the alternative hypothesis PFS6 being 0.5. As a result, the two-stage design required 6 or more patients among 15 treated patients achieve PFS6 to move to stage II, where additional 31 patients will be enrolled.

In light of the unexpected patient population that were treated in the NHMP cohort, the null and alternative hypotheses, as well as the two-stage design, should be adjusted to reflect the actual patient population. Based on the literature, PFS6 is 0.3 for grade 3 gliomas, and 0.1 for grade 4 glioblastoma. Thus, the updated null hypothesis for PFS6 = $(0.1 \times 8 + 0.3 \times 6) / (8 + 6) = 0.186$. Assuming 20% improvement as the original design, the alternative hypothesis for PFS6 is 0.386. Employing the Bayesian optimal phase 2 design, the updated 2-stage design becomes: enroll 15 patients, if there are 3 or more patients are progression-free at 6 months, move to stage II and enroll additional 15 patients. Among the total of 30 patients, if 10 or more patients are progression-free at 6 months, we claim that the treatment is promising for patients with NHMP IDH-mutant gliomas. This updated design yields 77.5% power, while controlling one-sided alpha at 0.05.

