2 ELIGIBILITY ASSESSMENT AND ENROLLMENT

2.1 ELIGIBILITY CRITERIA

2.1.1 Inclusion Criteria

- 2.1.1.1 Patients must have recurrent diffuse glioma (histologically confirmed by NIH Laboratory of Pathology) with *IDH1* or *IDH2* mutation (confirmed by DNA sequencing, FoundationOne is preferable for confirmation of mutation, but not necessary).
- 2.1.1.2 Patients must have tumor specific mutation burden (number of somatic mutations per exome) tested at NIH: Must have either result of tumor mutation burden from the most recent surgical tumor sample or must provide adequate genomic materials of the sample for tumor testing. The tumor tissue (e.g. block or 15 unstained slides) must be available for molecular and immune profiling. Fresh or frozen tumor sample will be used if available, but not mandatory.
- 2.1.1.3 Age ≥ 18 years. Because no dosing or adverse event data are currently available on the use of nivolumab in patients <18 years of age, children are excluded from this study, but will be eligible for future pediatric trials.
- 2.1.1.4 Patient must be able to tolerate an MRI study with intravenous gadolinium contrast.
- 2.1.1.5 Karnofsky $\geq 60\%$ ([Appendix A](#))
- 2.1.1.6 Patients must have adequate organ and marrow function as defined below:
 - Absolute neutrophil count $\geq 1,500/\text{mcL}$
 - Platelet Count $\geq 100,000/\text{mcL}$
 - Hemoglobin $> 9.0 \text{ g/dL}$ (may be transfused to achieve this level)
 - BUN $\leq 30 \text{ mg/dL}$ and

- Serum creatinine \leq 1.7 mg/dL
- Total bilirubin (except patients with Gilbert's Syndrome, who are eligible for the study but exempt from the total bilirubin eligibility criterion) \leq 2.0 mg/dL
- ALT **and** AST \leq 2.5x institutional upper limit of normal.

2.1.1.7 The effects of nivolumab on the developing human fetus are unknown. For this reason, women of child-bearing potential must agree to use adequate contraception (hormonal or barrier method of birth control; abstinence) prior to study entry and for the duration of study participation and up to 5 months (women). Should a woman become pregnant or suspect she is pregnant while she is participating in this study, she should inform her treating physician immediately.

2.1.1.8 The patient must be able to understand and be willing to sign a written informed consent document.

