10 STATISTICAL CONSIDERATIONS

10.1 STATISTICAL HYPOTHESIS

10.1.1 Primary Endpoint: PFS at 6 months

Hypothesis: The PFS6 for HMP cohort is 30% or better, and PFS6 for NHMP is 39% or better.

Simon's optimal two-stage design [57] will be used for conducting the trial for the HMP and NHMP cohorts independently. Specifically, for the HMP cohort, the null hypothesis is that the PFS6 is 0.1, and the alternative hypothesis is that the PFS6 is 0.3. The trial is carried out in two stages. In stage I, a total number of 10 patients is accrued. If 9 or more patients progressed by 6 months, the cohort will be terminated early; otherwise, additional 19 patients will be accrued in stage II, resulting in a total sample size of 29. Among these 29 patients, if 6 or more patients are progression-free at 6 months, we reject the null hypothesis and claim that the treatment is promising for patients with HMP IDH-mutant gliomas. The design controls the type I error rate at 0.05 and yields the power of 0.8.

For the NHMP cohort, the null hypothesis is that the PFS6 is 0.186, and the alternative hypothesis is that the PFS6 is 0.386. The trial is carried out in two stages. In stage I, a total number of 15 patients is accrued. If 3 or more patients are progression-free at 6 months, the cohort will be moved to stage II and additional 15 patients will be accrued in stage II, resulting in a total sample size of 30. Among these 30 patients, if 10 or more patients are progression-free at 6 months, we reject the null hypothesis and claim that the treatment is promising for patients with NHMP IDH-mutant gliomas. The design controls the type I error rate at 0.05 and yields the power of 0.8.

Rationale for the target PFS6 in HMP and NHMP cohorts:

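### Section 10 misstates the redesigned NHMP cohort: power is 0.775, not 0.8, the rationale and design name are out of date or in conflict, and the stated error rates lack the condition given in 1.2.7

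*Combined protocol and SAP*

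**What the plan says.** **Section 1.2.7** describes the redesign. Under version C, "the two-stage design required 6 or more patients among 15 treated patients achieve PFS6 to move to stage II", with 31 further patients to follow and hypotheses of 0.30 against 0.50. Six of 15 were progression-free, so that gate was met. The sponsor then looked at histology: "8 of the 15 patients had diagnosis of glioblastoma (WHO grade 4) prior to the study treatments", six had grade 3 tumours and one had grade II. From this it concluded that "the null and alternative hypotheses, as well as the two-stage design, should be adjusted to reflect the actual patient population". Taking it that "PFS6 is 0.3 for grade 3 gliomas, and 0.1 for grade 4 glioblastoma", the section derives a null of 0.186, adds 0.20 for the alternative, and adopts 3/15 then 10/30 using a Bayesian optimal phase 2 design. It concludes: "This updated design yields 77.5% power, while controlling one-sided alpha at 0.05".

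**Section 10.1.1** presents the NHMP design as Simon's optimal two-stage. It says "the null hypothesis is that the PFS6 is 0.186, and the alternative hypothesis is that the PFS6 is 0.386", gives the same 3/15 and 10/30 rule, and ends: "The design controls the type I error rate at 0.05 and yields the power of 0.8". The rationale that follows in 10.1.1 supports a P0 of 30% and a P1 of 50% for NHMP. It cites a glioblastoma PFS6 of 15% and then adopts 10% as the HMP null.

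**Section 10.1.1.1** gives 80% power with rates rounded to 0.19 and 0.39.

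Sections 10.1.1, 10.1.1.1 and 10.3.4 neither refer to 1.2.7 nor say that the rule followed the stage I result.

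**The concern.** The 10/30 rule is the NHMP success claim, and Section 10 is where a reader looks for its error rates. On four points that section does not describe the design now in force:

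- The power differs from the figure in 1.2.7 for the same rule and rates.
- The rationale supports hypotheses that are no longer tested, and none is given for those that are.
- Two design methods are named for one design.
- Error and power read as properties of a rule fixed before any NHMP result. In fact the null, the sample size and the cut-off were set with 6/15 known, and those patients count toward the 30.

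The last point matters because the stated 0.05 holds only if 0.186 is accepted as the right benchmark. That value is built from the grades of patients already treated and from a glioblastoma rate with no source. A report drawn from Section 10 alone would carry none of this.

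**Working it through.** **Inputs.** Stage I: 15 patients, continue with 3 or more. Final: 10 or more of 30. Null 0.186, alternative 0.386 (10.1.1 and 1.2.7); 0.19 and 0.39 (10.1.1.1). Version C gate: 6 or more of 15 (1.2.7).

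**Formula.** With X1 and X2 each binomial (15, p) and stage I gate g:

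P(success) = Σ over x from g to 15 of P(X1 = x) × P(X2 ≥ 10 − x).

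**Check of the method.** For HMP (2/10 then 6/29) the same calculation gives 0.047 at 0.1 and 0.805 at 0.3, matching the stated 0.05 and 0.8.

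**The plan's null.** (0.1×8 + 0.3×6)/14 = 2.6/14 = 0.186. Reproduced; the grade II patient is left out.

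**NHMP error and power, stated rule (g = 3)**

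| p | P(success) | Plan says |
|---|---|---|
| 0.186 (null) | 0.039 | at most 0.05 |
| 0.19 (rounded null) | 0.044 | at most 0.05 |
| 0.386 (alternative) | 0.775 | 77.5% in 1.2.7; 0.8 in 10.1.1 |
| 0.39 (rounded alternative) | 0.788 | 80% in 10.1.1.1 |

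The 77.5% of 1.2.7 is reproduced. Power of 0.80 is reached only at p = 0.394.

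**Design name.** A search over two-stage designs for 0.186 against 0.386 with error at most 0.05 and power at least 0.80 (total size up to 60) gives the smallest expected size under the null at 4/14 then 12/40 (error 0.041, power 0.803). The smallest total size that qualifies is 31. So 3/15 then 10/30 is not Simon's optimal design at the stated error and power.

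**Version C gate counted (g = 6).** If the cohort would have stopped below 6/15, error at 0.186 is 0.017. Power at 0.386 on that reading is 0.524, so 0.017 and 0.775 belong to different rules and should not be paired.

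**Dependence on the glioblastoma rate.** At 15%, the null is (0.15×8 + 0.3×6)/14 = 3.0/14 = 0.214. Error there is 0.088 (g = 3) or 0.041 (g = 6). With g = 3 the error reaches 0.05 at p = 0.1939, which corresponds to a glioblastoma rate of (0.1939×14 − 1.8)/8 = 0.114.

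**Dependence on grade mix.** Section 2.1.1 ("Patients must have recurrent diffuse glioma (histologically confirmed by NIH Laboratory of Pathology") sets no grade limit. Take rates of 0.1 and 0.3, and assume 0.3 for grade II, for which the documents give no rate. Error with g = 3 is then 0.016, 0.044 or 0.054 with 12, 8 or 7 grade 4 patients among the 15 in stage II. With g = 6 it is at most 0.035 for any mix.

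**The case against.** The strongest reply is that nothing is hidden. Section 1.2.7 sits in the same document and gives the 6/15 result, the old hypotheses, the grade counts, the formula and the 77.5%. That stands. The fault lies in Section 10's silence and its disagreement with 1.2.7. A reader might infer concealment, and the documents do not support that.

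A reader might also infer that type I error is inflated. At the stated null it is not: 0.039, or 0.017 with the version C gate counted, and 6/15 did meet that gate.

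A third tempting reading is that 1.2.7 uses 10% for glioblastoma while Section 10 uses 15%, so that the true error is 0.088. Section 10.1.1 cites 15% but then itself adopts 10% for the HMP null. Both places therefore work with 10%. What is missing is the step from 15% to 10%, and 0.088 is a sensitivity value, not the error of the stated design.

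The power gap is also small: 0.775 rounds to 0.8 at one decimal, and at the rounded 0.39 power is 0.788. But 1.2.7 reports to a tenth of a percent and 10.1.1.1 says 80%, so the sections disagree at the precision they use.

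**Conclusion.** The point holds as an error of statement in Section 10. Power is overstated by 2.5 percentage points at 0.386 (1.2 at 0.39). The rationale for 30% and 50% is superseded, and two design methods are named for one design. The condition on which the error rates rest appears only in 1.2.7.

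Type I error is controlled at 0.186, with a modest margin: it passes 0.05 at a null of about 0.194. These figures assume independent patients, 30 evaluable, and the exact binomial rule as written; the 0.017 also assumes that the cohort would have stopped with 3 to 5 of 15. The version C final cut-off is not in the documents, so how far the final criterion moved cannot be established.

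The documents do not support calling the 10/30 rule invalid, and they do not make a grade-standardised test necessary. Such a test would need a grade II reference rate that the plan does not contain.

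**What to change.** 1. In 10.1.1 and 10.1.1.1, state NHMP power as 0.775 at 0.386 and one-sided type I error as 0.039 at 0.186. Use 0.186 and 0.386 in both places and name one design method. Add that the null, sample size and rule were set after the stage I result of 6/15 was known, that those 15 patients count toward the 30 (see 1.2.7), and that the error rates are therefore conditional on 0.186.
2. In 10.1.1, replace the NHMP rationale for 30% and 50% with the rationale for 0.186 and 0.386.
3. Give the source for the 10% glioblastoma rate. Failing that, state as a sensitivity value that the error is about 0.088 at the cited 15% (null 0.214), or 0.041 with the version C gate counted.

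Leave the 10/30 rule unchanged. Reporting the WHO grade mix and PFS6 by grade descriptively is optional; no supportive grade-standardised p-value is required.

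The cost is amended wording in two sections and one reference or sentence, with no new patients. The stated power becomes slightly less favourable. The change does not undo the reuse of stage I; it puts the condition next to the error rate.
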